3.2. ASSESSMENT OF CAUSALITY

Investigators should use their knowledge of the participant, the circumstances surrounding the event, and an evaluation of any potential alternative causes to determine whether or not an adverse event is considered to be related to the study treatment, indicating "yes" or "no" accordingly. The following guidance should be taken into consideration:

- Temporal relationship of event onset to the initiation of study treatment.
- Course of the event, considering especially the effects of, discontinuation of study treatment, or reintroduction of study treatment.
- Known association of the event with the study treatment or with similar treatments.
- Known association of the event with the disease under study.

- Presence of risk factors in the participant or use of concomitant medications known to increase the occurrence of the event.
- Presence of non-treatment-related factors that are known to be associated with the occurrence of the event.

For participant receiving combination therapy, causality will be assessed individually for each protocol-mandated therapy.

4. FOLLOW-UP OF AES AND SAES

The Investigator is obligated to perform or arrange for the conduct of supplemental measurements and/or evaluations as medically indicated or as requested by the Sponsor or its delegate to elucidate the nature and/or causality of the AE or SAE as fully as possible. This may include additional laboratory tests or investigations, histopathological examinations, or consultation with other health care professionals.

If a participant dies during participation in the study or during a recognized follow-up period, the Investigator will provide the Sponsor with a copy of any post-mortem findings including histopathology.

New or updated information will be recorded in the originally completed eCRF.

The Investigator will submit any updated SAE data to the Sponsor within 24 hours of receipt of the information.

5. IMMEDIATE REPORTING REQUIREMENTS FROM INVESTIGATOR TO SPONSOR

Certain events require immediate reporting to allow the Sponsor to take appropriate measures to address potential new risks in a clinical trial. The Investigator must report such events to the Sponsor immediately; under no circumstances should reporting take place more than 24 hours after the Investigator learns of the event. The following is a list of events that the Investigator must report to the Sponsor within 24 hours after learning of the event, regardless of relationship to study treatment:

- Serious adverse events
- Non-serious adverse events of special interest (NSAESI)
- Pregnancies (see Section [8.3.5](#))

The Investigator must report new significant follow-up information for these events to the Sponsor immediately (i.e., no more than 24 hours after becoming aware of the information). New significant information includes the following:

- New signs or symptoms or a change in the diagnosis.
- Significant new diagnostic test results.

- Change in causality based on new information.
- Change in the event's outcome, including recovery.
- Additional narrative information on the clinical course of the event.

Investigators must also comply with local requirements for reporting serious adverse events to the local Health Authority and IRB/EC.

5.1 REPORTING REQUIREMENTS OF SERIOUS ADVERSE EVENTS, AND NON-SERIOUS ADVERSE EVENTS OF SPECIAL INTEREST

Events that Occur prior to Study Treatment Initiation

After informed consent has been obtained but prior to initiation of study treatment, only serious adverse events caused by a protocol-mandated intervention should be reported. The Serious Adverse Event/Adverse Event of Special Interest Reporting Form provided to Investigators should be completed and submitted to the Serious Adverse Event Responsible immediately (i.e., no more than 24 hours after learning of the event).

Events that Occur after Study Treatment Initiation

For reports of serious adverse events and non-serious adverse events of special interest (Section 8.3.6) that occur after initiation of study treatment (Section 8.3.1), Investigators should record all case details that can be gathered immediately (i.e., within 24 hours after learning of the event) on the appropriate Adverse Event of Special Interest/ Serious Adverse Event eCRF form and submit the report via the electronic data capture (EDC) system. A report will be generated and sent to the Sponsor's Safety Risk Management department.

In the event that the EDC system is unavailable, the Serious Adverse Event/Adverse Event of Special Interest Reporting Form provided to Investigators should be completed and submitted to the Serious Adverse Event Responsible immediately (i.e., no more than 24 hours after learning of the event).

Once the EDC system is available, all information will need to be entered and submitted via the EDC system.

Reporting of Post-Study Adverse Events and Serious Adverse Events

If the Investigator becomes aware of any other serious adverse event occurring after the end of the AE reporting period, if the event is believed to be related to prior study treatment the event should be reported directly to the Sponsor or its designee, either by faxing or by scanning and emailing the SAE Reporting Form using the fax number or email address provided to Investigators.

5.2 REPORTING REQUIREMENTS FOR CASES OF ACCIDENTAL OVERDOSE OR MEDICATION ERROR

Accidental overdose and medication error (hereafter collectively referred to as "special situations"), are defined as follows:

- Accidental overdose: accidental administration of a drug in a quantity that is higher than the assigned dose,
- Medication error: accidental deviation in the administration of a drug,
In some cases, a medication error may be intercepted prior to administration of the drug.

Special situations are not in themselves adverse events, but may result in adverse events. Each adverse event associated with a special situation should be recorded separately on the Adverse Event eCRF. If the associated adverse event fulfills seriousness criteria, the event should be reported to the Sponsor immediately (i.e., no more than 24 hours after learning of the event). For RO7049665/placebo, adverse events associated with special situations should be recorded as described below for each situation:

- Accidental overdose: Enter the adverse event term. Check the "Accidental overdose" and "Medication error" boxes.
- Medication error that does not qualify as an overdose: Enter the adverse event term. Check the "Medication error" box.
- Medication error that qualifies as an overdose: Enter the adverse event term. Check the "Accidental overdose" and "Medication error" boxes.

In addition, all special situations associated with RO7049665/placebo, regardless of whether they result in an adverse event, should be recorded on the Adverse Event eCRF and should be recorded as described below:

- Accidental overdose: Enter the drug name and "accidental overdose" as the event term. Check the "Accidental overdose" and "Medication error" boxes.
- Medication error that does not qualify as an overdose: Enter the name of the drug administered and a description of the error (e.g., wrong dose administered, wrong dosing schedule, incorrect route of administration, wrong drug, expired drug administered) as the event term. Check the "Medication error" box.
- Medication error that qualifies as an overdose: Enter the drug name and "accidental overdose" as the event term. Check the "Accidental overdose" and "Medication error" boxes. Enter a description of the error in the additional case details.
- Intercepted medication error: Enter the drug name and "intercepted medication error" as the event term. Check the "Medication error" box. Enter a description of the error in the additional case details.

As an example, an accidental overdose that resulted in a headache would require the completion of two Adverse Event eCRF pages, one to report the accidental overdose and one to report the headache. The "Accidental overdose" and "Medication error" boxes would need to be checked on both eCRF pages.

6. EXPEDITED REPORTING TO HEALTH AUTHORITIES, INVESTIGATORS, INSTITUTIONAL REVIEW BOARDS, AND ETHICS COMMITTEES

The Sponsor will promptly evaluate all serious adverse events and NSAESI against cumulative product experience to identify and expeditiously communicate possible new safety findings to Investigators, IRBs, ECs, and applicable Health Authorities based on applicable legislation.

To determine reporting requirements for single adverse event cases, the Sponsor will assess the expectedness of these events through use of the reference safety information in the document listed below:

Study Treatment	Document
RO7049665	RO7049665 Investigator's Brochure

The Sponsor will compare the severity of each event and the cumulative event frequency reported for the study with the severity and frequency reported in the applicable reference document.

Reporting requirements will also be based on the Investigator's assessment of causality and seriousness, with allowance for upgrading by the Sponsor as needed.

Appendix 3

Procedures for Recording Adverse Events

Investigators should use correct medical terminology/concepts when recording adverse events on the Adverse Event eCRF. Avoid colloquialisms and abbreviations.

Only one adverse event term should be recorded in the event field on the Adverse Event eCRF.

1. DIAGNOSIS VERSUS SIGNS AND SYMPTOMS

1.1. INJECTION REACTIONS

Adverse events that occur during or after study treatment administration and are judged to be related to study treatment injection should be captured as a diagnosis (e.g., injection-related reaction or injection-site reaction) on the Adverse Event eCRF. If possible, avoid ambiguous terms such as “systemic reaction”. Associated signs and symptoms should be recorded on the dedicated Injection Reaction eCRF. If a participant experiences both a local and systemic reaction to the same dose of study treatment, each reaction should be recorded separately on the Adverse Event eCRF, with signs and symptoms also recorded separately on the dedicated Injection Reaction eCRF.

1.2. OTHER ADVERSE EVENTS

For adverse events other than injection reactions, a diagnosis (if known) should be recorded on the Adverse Event eCRF rather than individual signs and symptoms (e.g., record only liver failure or hepatitis rather than jaundice, asterixis, and elevated transaminases). However, if a constellation of signs and/or symptoms cannot be medically characterized as a single diagnosis or syndrome at the time of reporting, each individual event should be recorded on the Adverse Event eCRF. If a diagnosis is subsequently established, all previously reported adverse events based on signs and symptoms should be nullified and replaced by one adverse event report based on the single diagnosis, with a starting date that corresponds to the starting date of the first symptom of the eventual diagnosis.

2. ADVERSE EVENTS OCCURRING SECONDARY TO OTHER EVENTS

In general, adverse events occurring secondary to other events (e.g., cascade events or clinical sequelae) should be identified by their primary cause, with the exception of severe or serious secondary events. However, medically significant adverse events occurring secondary to an initiating event that are separated in time should be recorded as independent events on the Adverse Event eCRF. For example:

- If vomiting results in mild dehydration with no additional treatment in a healthy adult, only vomiting should be reported on the eCRF.

- If vomiting results in severe dehydration, both events should be reported separately on the eCRF.
- If a severe gastrointestinal hemorrhage leads to renal failure, both events should be reported separately on the eCRF.
- If dizziness leads to a fall and subsequent fracture, all three events should be reported separately on the eCRF.

All adverse events should be recorded separately on the Adverse Event eCRF if it is unclear as to whether the events are associated.

3. PERSISTENT OR RECURRENT ADVERSE EVENTS

A persistent adverse event is one that extends continuously, without resolution, between participant evaluation time-points. Such events should only be recorded once on the Adverse Event eCRF. The initial severity of the event should be recorded, and the severity should be updated to reflect the most extreme severity any time the event worsens. If the event becomes serious, the Adverse Event eCRF should be updated to reflect this.

A recurrent adverse event is one that resolves between participant evaluation time-points and subsequently recurs. Each recurrence of an adverse event should be recorded separately on the Adverse Event eCRF.

4. ABNORMAL LABORATORY VALUES

Not every laboratory abnormality qualifies as an adverse event. A laboratory test result should be reported as an adverse event if it meets any of the following criteria:

- Accompanied by clinical symptoms.
- Results in a change in study treatment (e.g., dosage modification, treatment interruption, or treatment discontinuation).
- Results in a medical intervention (e.g., potassium supplementation for hypokalemia) or a change in concomitant therapy.
- Clinically significant in the Investigator's judgment.

It is the Investigator's responsibility to review all laboratory findings. Medical and scientific judgment should be exercised in deciding whether an isolated laboratory abnormality should be classified as an adverse event.

If a clinically significant laboratory abnormality is a sign of a disease or syndrome (e.g., alkaline phosphatase and bilirubin 5 times the upper limit of normal (ULN) associated with cholecystitis), only the diagnosis (i.e., cholecystitis) should be recorded on the Adverse Event eCRF.

If a clinically significant laboratory abnormality is not a sign of a disease or syndrome, the abnormality itself should be recorded on the Adverse Event eCRF, along with a descriptor indicating if the test result is above or below the normal range (e.g., "elevated potassium", as opposed to "abnormal potassium"). If the laboratory abnormality can be characterized by a precise clinical term per standard definitions, the clinical term should be recorded as the adverse event. For example, an elevated serum potassium level of 7.0 mEq/L should be recorded as "hyperkalemia".

Observations of the same clinically significant laboratory abnormality from visit to visit should not be repeatedly recorded on the Adverse Event eCRF, unless the etiology changes. The initial severity of the event should be recorded, and the severity or seriousness should be updated any time the event worsens.

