8.1 EFFICACY ASSESSMENTS

The primary efficacy endpoint of this study is time from randomization to relapse. Relapse is defined in Table 8. ALT and IgG will be assessed centrally according to the SoA (see Section 1.3). If a value exceeds the defined threshold, the site will be notified immediately, and a confirmatory sample will be taken no less than 7 days after the sample showing exceeding the threshold the first time. If the values returned to below the threshold in the repeat measurement, the participant can continue in the study. If the values still exceed the threshold, the participant can be either re-tested (as described in Table 8) or will be counted as having a relapse and leave the study, depending on the test results. SoC should be started as soon as relapse is confirmed.

If CCSs are increased during tapering or re-introduced because of AIH flare as per Investigator assessment (e.g., ALT > 1 and < 2 for extended period or biopsy finding), the incidence will be counted as an event, and the respective participant should stop study treatment.

Changes in ALT, AST, and IgG will be assessed according to the SoA (Section 1.3).

Table 8 Decision Tree for ALT or IgG Increase

ALT $\geq 2 \times$ ULN < $5 \times$ ULN	Confirm +7 days	
 – If < $2 \times$ ULN \rightarrow return to normal schedule – If $\geq 2 \times$ ULN and < $3 \times$ ULN \rightarrow retest + 7 days \rightarrow if not < $2 \times$ ULN = relapse: end of study – If $\geq 3 \times$ ULN \rightarrow relapse: end of study
ALT $\geq 5 \times$ ULN	Relapse: end of study	
IgG > $1 \times$ ULN < $1.5 \times$ ULN	Confirm +14 days	
 – If $\leq 1 \times$ ULN \rightarrow return to normal schedule – If > $1 \times$ ULN and < $1.5 \times$ ULN \rightarrow retest + 14 days; if > $1 \times$ ULN \rightarrow relapse: end of study – If $\geq 1.5 \times$ ULN \rightarrow relapse; end of study
IgG $\geq 1.5 \times$ ULN	Relapse: end of study	

Study treatment continues as per SoA (see Section 1.3) until relapse criteria are met.

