8.2.4 Clinical Safety Laboratory Assessments

Normal ranges for the study laboratory parameters must be supplied to the Sponsor before the study starts. A list of clinical laboratory tests to be performed is provided in [Appendix 4](#) and these assessments must be conducted in accordance with the separate laboratory manual and the SoA (Section 1.3).

The Investigator must review the laboratory report, document this review, and record any clinically relevant changes occurring during the study in the AE section of the CRF. The laboratory reports must be filed with the source documents. Clinically significant abnormal laboratory findings are those which are not associated with the underlying disease, unless judged by the Investigator to be more severe than expected for the participant's condition.

- In the event of unexplained abnormal clinically significant laboratory test values, the tests should be repeated immediately and followed up until they have returned to the normal range and/or an adequate explanation of the abnormality is found.
- If such values do not return to normal/baseline within a period of time judged reasonable by the Investigator, the etiology should be identified and the Sponsor notified.
- If laboratory values from non-protocol-specified laboratory assessments performed at the local laboratory require a change in participant management or are considered clinically significant by the Investigator (e.g., SAE or AE or dose-modification) then, the results must be recorded in the CRF/Clinical Trial Adverse Event/Special Situations Form.

Results of clinical laboratory testing will be recorded on the eCRF or be received as electronically produced laboratory reports submitted directly from the local or central laboratory.

Additional blood or urine samples may be taken at the discretion of the Investigator if the results of any test fall outside the reference ranges, or clinical symptoms necessitate additional testing to monitor participant safety.

Where the clinical significance of abnormal laboratory results at screening is considered uncertain, screening laboratory tests may be repeated before randomization to confirm eligibility.

If there is an alternative explanation for a positive urine or blood test for drugs of abuse, e.g., previous occasional intake of a medication or food containing for example, codeine, benzodiazepines or opiates, the test could be repeated to confirm washout.

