9.2 SAMPLE SIZE DETERMINATION

The sample size for this study is based on independent pairwise comparisons of each RO7049665 group—i.e., high dose (7.5 mg) and low dose (3.5 mg) with placebo. The total sample size required is obtained by multiplying the appropriate per-group size by three. Methods for the control of the family-wise error rate are described both in this section and in Section 9.3.

The reference treatment effect is 0.272. The study will use an overall one-sided type 1 error rate (significance level) of 2.5%. A power of 90% against the reference treatment effect is required.

There will be one opportunity to stop for success before the end of the study, at 50% information. An O'Brien-Fleming-like alpha-spending rule will preserve the type 1 error rate. The success boundary will be binding.

There will be two opportunities to stop for futility before the end of the study: once at 25% information (i.e., when 25% of the maximum number of events have occurred) and once at 50% information (i.e. when 50% of the maximum number of events have occurred). A Pocock-like beta-spending rule will preserve power of the study. The futility boundary will be non-binding.

If the proportional hazards assumption holds, these assumptions imply that 29.1 events (i.e., 30 events for all practical purposes) in the placebo and 7.5 mg RO7049665 arms combined are required to achieve the desired power and significance levels.

Under the assumption that recruitment to the study will take approximately 19 months, that sites will be activated at uniform rate for six months, after which recruitment will plateau, and that follow-up should continue for at most 6 months after the last patient to enter the study is randomized, then recruitment of 28 participants per arm will generate the required number of events.

Table 9 Summary of the Group Sequential Design

Stage	Interim 1	Interim 2	End of study
Information rate	25%	50%	100%
Efficacy boundary (z-value scale)	∞	2.963	1.969
Futility boundary (z-value scale)	-0.046	0.738	
Number of subjects ^{a,c}	31	47	56
Cumulative number of events ^a	7.3	14.5	29.1
Analysis time ^{b,c}	11.7	16.3	25.0
Cumulative alpha spent	<0.0001	0.0015	0.025
Cumulative power	<0.0001	0.3159	0.9000
One-sided local significance level	N/A	0.0015	0.0245 ^d
Efficacy boundary (t)	N/A	0.211	0.482
Futility boundary (t)	1.035	0.679	
Overall exit probability (under H0)	0.4815	0.3136	
Exit probability for efficacy (under H0)	<0.0001	0.0015	

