9.5.3 Safety Analyses

All safety analyses (see [Table 11](#)) will be based on the safety analysis population grouped according to the treatment assigned at randomization (see [Table 10](#)).

Table 11 Safety Statistical Analysis Methods

Endpoint	Statistical Analysis Methods
Adverse events	
The original terms recorded on the eCRF by the Investigator for AEs will be coded by the Sponsor.
 
Adverse events will be summarized by mapped term and appropriate thesaurus level. Incidence, nature and severity of AEs, number of participants with SAEs, treatment-related SAEs, SAEs leading to discontinuation, treatment-related AEs, or AEs leading to discontinuation will be tabulated.

Clinical laboratory tests	
All clinical laboratory data will be stored on the database in the units in which they were reported. Laboratory test values will be presented in International System of Units (SI units; Système International d'Unités) by individual outputs with flagging of abnormal results. In addition, tabular summaries will be used, as appropriate. Laboratory data not reported in SI units will be converted to SI units before processing.

Vital signs	
Vital signs data and weight data will be presented with flagging of values outside the normal ranges and flagging of abnormalities. In addition, tabular summaries will be used, as appropriate.

ECG data analysis	
ECG data will be presented using appropriate outputs, with flagging of values outside the normal ranges and abnormalities. In addition, tabular summaries will be used, as appropriate.

Concomitant medications	
The original terms recorded on the participants' eCRF by the Investigator for concomitant medications will be standardized by the Sponsor by utilizing a mapped term and appropriate drug dictionary level.
 
Concomitant medications will be presented using appropriate outputs.

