1. DEFINITION OF ADVERSE EVENTS

According to the E2A ICH guideline for Good Clinical Practice, an **adverse event** is any untoward medical occurrence in a participant or clinical investigation participant administered a pharmaceutical product and which does not necessarily have to have a causal relationship with this treatment.

An adverse event can therefore be:

- Any unfavorable and unintended sign (including an abnormal laboratory finding), symptom, or disease temporally associated with the use of a medicinal product, whether or not considered related to the medicinal product.

Events Meeting the AE Definition:

- Deterioration in a laboratory value (hematology, clinical chemistry, or urinalysis) or other clinical test (e.g., ECG, x-ray) that is associated with symptoms or leads to a change in study treatment or concomitant treatment or discontinuation from study treatment (see [Appendix 3](#), Section 4).
- Exacerbation of a chronic or intermittent preexisting condition, including either an increase in frequency and/or intensity of the condition.
- New conditions detected or diagnosed after study treatment administration even though it may have been present before the start of the study.
- Adverse events that are related to a protocol-mandated intervention, including those that occur prior to assignment of study treatment (e.g., screening invasive procedures such as biopsies).
- "Lack of efficacy" or "failure of expected pharmacological action" per se will not be reported as an AE or SAE unless the relapse is unexpectedly accelerated and not in line with the natural history of the disease. If the "Lack of efficacy" would not require safety reporting such instances will be captured in the efficacy assessments. However, the signs, symptoms, and/or clinical sequelae resulting from lack of efficacy will be reported as AE or SAE if they fulfill the definition of an AE or SAE.

Events NOT Meeting the AE Definition:

- Any clinically significant abnormal laboratory findings or other abnormal safety assessments which are associated with the underlying disease, unless judged by the Investigator to be more severe than expected for the participant's condition.
- The disease/disorder being studied or expected progression, signs, or symptoms of the disease/disorder being studied, unless more severe than expected for the participant's condition.

- Medical or surgical procedure (e.g., endoscopy, appendectomy): the condition that leads to the procedure is an AE.

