9. LACK OF EFFICACY OR WORSENING OF AUTOIMMUNE HEPATITIS

Medical occurrences or symptoms of deterioration that are anticipated as part of AIH should be recorded as an adverse event if judged by the Investigator to have

unexpectedly worsened in severity or frequency or changed in nature at any time during the study. When recording an unanticipated worsening of AIH on the Adverse Event eCRF, it is important to convey the concept that the condition has changed by including applicable descriptors (e.g., “accelerated Auto Immune Hepatitis”).

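### The AE-recording rules conflict for a laboratory-defined relapse, so the count of AEs leading to discontinuation depends on which rule a site applies

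*Combined protocol and SAP*

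**What the plan says.** **What a relapse triggers.** Table 8 in Section 8.1 defines relapse by ALT or IgG thresholds. Sections 4.1.3 and 7.1 list relapse as a reason to stop study treatment, and Section 8.1 adds: "SoC should be started as soon as relapse is confirmed".

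**Rules that make it an AE.**
- Appendix 3 section 4: "A laboratory test result should be reported as an adverse event if it meets any of the following criteria". The list includes a change in study treatment, with discontinuation as an example, and a change in concomitant therapy.
- Appendix 2 section 1, first bullet of events that meet the definition: a laboratory deterioration that "leads to a change in study treatment or concomitant treatment or discontinuation from study treatment". It cross-refers to Appendix 3 section 4.

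**Rules that exclude it.**
- Appendix 2 section 1, events that do not meet the definition: "Any clinically significant abnormal laboratory findings or other abnormal safety assessments which are associated with the underlying disease", unless judged more severe than expected.
- Section 8.2.4: "Clinically significant abnormal laboratory findings are those which are not associated with the underlying disease", with the same exception.
- Appendix 3 section 9: "symptoms of deterioration that are anticipated as part of AIH should be recorded as an adverse event if judged by the Investigator" to have worsened unexpectedly or changed in nature.

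**A rule that points both ways.** The lack-of-efficacy bullet in Appendix 2 section 1 says lack of efficacy is not in itself an AE unless relapse is unexpectedly accelerated. It then has the resulting signs and sequelae reported if they meet the AE definition.

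**Where it is counted.** Table 11 in Section 9.5.3: "treatment-related AEs, or AEs leading to discontinuation will be tabulated". It does not separate out relapse.

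**The concern.** The primary efficacy event is itself a laboratory abnormality, and it is the exit the design expects most often. One set of rules makes it an AE leading to discontinuation; the other does not make it an AE unless it is worse than expected. AE incidence and severity is a secondary endpoint in Table 5. The plan assumes three times as many relapses on placebo as on active at 6 months. Recording relapses as AEs therefore adds efficacy failures mainly to the placebo column and can hide an excess of true intolerance on RO7049665. If sites differ, the table mixes the two conventions in unknown proportion.

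**Working it through.** **1. The texts set against a confirmed Table 8 relapse.**

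| Rule | Result for an ordinary relapse |
|---|---|
| Appendix 3 section 4, criteria list | AE: study drug stops and SoC starts |
| Appendix 2 section 1, first bullet | AE: same trigger |
| Appendix 2 section 1, exclusion list | Not an AE unless more severe than expected |
| Section 8.2.4 | Not a clinically significant finding unless more severe than expected |
| Appendix 3 section 9 | By implication, recorded only if the worsening is unexpected |
| Lack-of-efficacy bullet | Not an AE in itself, but its signs return to the AE definition |

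The last row sends the reader back to the second, so it does not settle the matter. The conflict lies within Appendix 2 as well as between the appendices.

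**2. The plan's own figures.** Inputs from Sections 9.1 and 9.2: 6-month relapse of 45% and 15%, exponential times, 28 per arm, 19 months' recruitment with a 6-month ramp, analysis at month 25.
- Placebo hazard: −ln(0.55)/6 = 0.0996 per month, mean 10.0 months.
- Active hazard: −ln(0.85)/6 = 0.0271 per month, mean 36.9 months.
- Hazard ratio: 0.0271/0.0996 = 0.272.

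All agree with Section 9.1.

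**3. Expected relapses per arm, relapse the only exit.**
- At 6 months: 28 × 0.45 = 12.6 and 28 × 0.15 = 4.2.
- At month 25: take accrual intensity a(t) = t/6 up to month 6 and 1 from then to month 19, with total 3 + 13 = 16. P(relapse) = 1 − (1/16)∫a(t)exp(−λ(25 − t))dt.
  - Placebo: 1 − (0.374 + 4.008)/16 = 0.726, so 20.3 relapses.
  - Active: 1 − (1.700 + 9.314)/16 = 0.312, so 8.7 relapses.
  - The unrounded sum is 29.06, against 29.1 in Table 9.

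These are upper limits for laboratory-defined relapse, because treatment-related discontinuation and AIH-related CCS increases also count as events in Table 6.

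**4. Effect on AE discontinuations at 6 months.** The documents give no non-relapse AE-discontinuation rates, so these are assumed: 0% on placebo and d on active. Let x be the share of relapses recorded as AEs. With competing exponential exits on active:
- P(any exit) = 1 − (1 − d)(0.85).
- P(AE exit first) = P(any exit) × ln(1 − d)/[ln(1 − d) + ln(0.85)].
- Table entry on active = P(AE first) + x·P(relapse first); on placebo = 0.45x.

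For d = 10%, P(any exit) = 0.235, P(AE first) = 0.092 and P(relapse first) = 0.143. For d = 30% they are 0.405, 0.278 and 0.127.

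| x | Placebo | Active, d = 10% | Active, d = 30% |
|---|---|---|---|
| 0 | 0% | 9.2% | 27.8% |
| 0.25 | 11.3% | 12.8% | 31.0% |
| 0.5 | 22.5% | 16.4% | 34.2% |
| 1 | 45.0% | 23.5% | 40.5% |

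The sign changes at x = 0.092/(0.45 − 0.143) ≈ 0.30 for d = 10%, and at x = 0.278/(0.45 − 0.127) ≈ 0.86 for d = 30%.

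**5. Non-zero placebo rate.** Here the entry is 28 × [1 − (1 − d)(1 − x·r)], with r the relapse probability; placebo is given first.
- Assumed 5% versus 10%: 1.4 versus 2.8 participants with none recorded, 4.4 versus 3.7 with a quarter recorded, and 13.4 versus 6.6 with all recorded at 6 months. At month 25, all recorded gives 20.7 versus 10.7.
- Assumed 5% versus 20%: 1.4 versus 5.6 with none recorded, 7.4 versus 7.3 with half recorded, and 13.4 versus 9.0 with all recorded at 6 months.

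**6. Any-AE incidence, all relapses recorded.** Same formula as proportions, with d now the assumed any-AE rate.

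| Assumed placebo versus active | 6 months | Month 25 |
|---|---|---|
| 50% versus 70% | 72.5% versus 74.5% | 86% versus 79% |
| 60% versus 80% | 78% versus 83% | 89% versus 86% |
| 70% versus 90% | 83.5% versus 91.5% | 92% versus 93% |

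The sign reverses in two of the six cells, both at month 25.

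**The case against.** The strongest reply is that Appendix 2 deals with relapse by name: lack of efficacy is not in itself an AE and is captured in the efficacy assessments. A study-specific rule can fairly be read as overriding generic laboratory bullets. That reading is reasonable, but the sentence that follows returns the signs to the AE definition, and the first bullet of that definition is met by any relapse that stops study drug.

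A reader might infer that Appendix 3 makes every relapse an AE. It does not. Section 4 opens by saying that not every abnormality qualifies, asks for medical judgment, and has only the diagnosis recorded when a value is a sign of disease; section 9 then applies to AIH worsening. These clauses stand, but they leave the decision to each site. Recording the diagnosis changes the AE term without deciding whether there is an AE.

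A reader might also infer that Appendix 2 is wholly on the excluding side, or that it admits no relapse as an AE. Its first bullet and its exceptions for accelerated or more severe relapse show otherwise.

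Nor are the safety data beyond interpretation. Section 7.1 records the primary reason for stopping, with relapse among the listed reasons; Section 9.7 summarizes discontinuations; Table 11 works by mapped term and separates treatment-related events. Relapse stops can therefore be identified at analysis. What remains is that Table 11 does not commit to doing so, and that the AE rows themselves may follow different conventions.

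**Conclusion.** The conflict is real and unresolved in the text. Its direct size is at most 12.6 placebo versus 4.2 active relapses per arm at 6 months, or 20.3 versus 8.7 at month 25, on the plan's relapse rates and accrual with relapse as the only exit.

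A reader might infer that the tolerability comparison will be reversed. The documents do not support that as a general statement, because it needs non-relapse discontinuation rates they do not supply and a large enough share of relapses recorded. At an assumed 0% versus 10%, reversal needs about 30% of relapses recorded; at 0% versus 30% it needs about 86%. Any-AE incidence is less sensitive.

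Nor does the conflict reach the primary analysis: relapse counts as an event under Section 8.1 however it is recorded for safety, so alpha and power are unaffected. Section 9.5.2.2 plans no formal test of secondary endpoints. The matter should be corrected because it can bias a descriptive secondary safety endpoint in the first study of this drug in AIH.

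**What to change.** Reconcile Section 8.2.4, Appendix 2 section 1 (both lists and the lack-of-efficacy bullet) and Appendix 3 sections 4 and 9 into one recording rule: a protocol-defined relapse is not an AE solely because it stops study drug or starts SoC. Editing Appendix 3 alone would leave the conflict inside Appendix 2.

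Keep AE reporting where the event is serious, meets the liver-test criteria in Appendix 3 section 6, is accelerated or worse than expected, or is suspected to be caused by study drug. The last condition is needed because Table 8 is purely numerical and does not ask why ALT rose; a blanket exemption could remove a drug-induced rise from the AE data.

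In Table 11, add a separate row for discontinuation due to AIH relapse, and show AEs leading to discontinuation with and without relapse.

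The cost is protocol and eCRF-guideline wording and a few table rows. Relapses remain captured as efficacy events. The downside is that some ALT and IgG rises would no longer appear as AE rows.
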